4.4.2 Summaries of Demographics and Baseline Characteristics

Demographic variables and other baseline and disease characteristics will be summarized overall and by randomized treatment sequence using descriptive statistics on the FAS.

A summary of concordance of stratification factors determined by eCRF versus IxRS will also be reported.

4.4.3 Exploratory Pharmacokinetic Analyses

Samples will be collected for PK analyses and to compare exposure in this study with that attained in previous studies. Serum concentrations of atezolizumab will be reported as individual values and summarized (mean, standard deviation, coefficient of variation, median, range, geometric mean, and geometric mean coefficient of variation) by treatment arm and cycle, when appropriate and as data allow. Individual and median serum atezolizumab concentrations will be plotted by treatment arm and day.

Atezolizumab concentration data may be pooled with data from other studies using an established population PK model to derive PK parameters such as clearance, volume of distribution, and area under the curve, as warranted by the data. Potential correlations of relevant PK parameters with safety outcomes may be explored.

PK analyses will be based on the PK-evaluable population.

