Atezolizumab will be administered on Day 1 of each 21-day cycle. Participants will receive atezolizumab according to their assigned route of administration (i.e., SC or IV) for the first three treatment cycles. At Cycle 4, participants will cross-over and receive atezolizumab administered according to the alternative route of administration for Cycles 4–6. This period of 3+3 cycles in both treatment arms constitutes the study Treatment Cross-over Period.

After Cycle 6, participants will select how they would like atezolizumab to be administered (SC or IV) for the Treatment Continuation Period. The Treatment Continuation Period will continue until Cycle 16 for participants with early-stage NSCLC or until loss of clinical benefit, as determined by the investigator according to local standard of care, for patients with advanced NSCLC.

Participants will undergo an End of Treatment Visit within 30 days after completing study treatment and will enter *the safety follow-up period*. *Safety follow-up should occur approximately 90 days after the last dose of study treatment. Thereafter, participants will be contacted for survival status and to collect details of new anti-cancer therapy, if any.*

Participant preference will be assessed based on the PPQ (administered following treatment administration on Day 1, Cycle 6 of the Treatment Cross-over Period). Treatment satisfaction will be assessed based on the TASQ (administered following treatment administration on Day 1 of Cycles 3 and 6 of the Treatment Cross-over Period). Healthcare professionals will record their perception of time/resource use and convenience of treatment administration completing the HCPQs. Perception of time/resource use will be captured during the Treatment Cross-over Period and perception of convenience will be captured after administration of each participant's treatment Cycle 6. Health-related quality of life will be assessed using the EORTC QLQ-C30 completed during the Treatment Cross-over Period (at Cycle 1, Cycle 3, and Cycle 6), during the Treatment Continuation Period (at Cycle 7, Cycle 10, Cycle 13, and Cycle 16), and at the end of study treatment visit. Health utilities will be collected using the EQ-5D-5L questionnaire at the same time points as the EORTC QLQ-C30. The study questionnaires are provided in [Appendix 4](#), [Appendix 5](#), and [Appendix 6](#).

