Appendix 1: Schedule of Activities

Preparation Area). Instructions for which questions should be completed in each questionnaire at each timepoint are indicated in the introduction to each questionnaire.

- ^{aa} Medication (e.g., prescription drugs, over-the-counter drugs, vaccines, herbal or homeopathic remedies, nutritional supplements) used by a participant in addition to protocol-mandated treatment from 7 days prior to initiation of study treatment until the treatment discontinuation visit.
- ^{bb} After informed consent has been obtained but prior to initiation of study treatment, only serious adverse events caused by a protocol-mandated intervention should be reported. After initiation of study treatment, all adverse events will be reported until 30 days after the final dose of study treatment or until initiation of new systemic anti-cancer therapy, whichever occurs first, and serious adverse events and adverse events of special interest will continue to be reported until 90 days after the final dose of study treatment or until initiation of new systemic anti-cancer therapy, whichever occurs first. After this period, all deaths, regardless of cause, should be reported. In addition, the Sponsor should be notified if the investigator becomes aware of any serious adverse event that is believed to be related to prior exposure to study treatment (see Section 5.6).
- ^{cc} Participants should receive their first dose of study drug on the day of randomization, if possible. If this is not possible, the first dose should occur no later than 5 days after enrollment. For administration instructions, please check the Pharmacy Manual.
- ^{dd} After Cycle 6, participants will select the route of administration (SC or IV) they would like to receive from Cycle 7 onwards.

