
 Evaluate HCP perception of time/resource use and convenience for administration with atezolizumab SC and IV 	
 HCP responses to the Healthcare Professional Questionnaires (HCPQs), by individual question

 Evaluate HRQoL with atezolizumab SC and atezolizumab IV 	
 Change in symptoms and function from baseline and over time as assessed by European Organization for Research and Treatment of Cancer Quality of Life Questionnaire C30 (EORTC QLQ-C30) scores

	
 • Mean and mean changes from baseline score in HRQoL by cycle as assessed by the Global Health Status/Quality of Life (GHS/QoL) scale (items 29 and 30) of the EORTC QLQ-C30

 • Monitor the ongoing clinical benefit of atezolizumab 	
 • Proportion of participants with continuing clinical benefit after 16 cycles of atezolizumab, as assessed by the investigator according to local standard of care
Safety Objectives	Corresponding Endpoints

 • Evaluate the overall safety and tolerability of atezolizumab SC and atezolizumab IV 	
 • Incidence, severity, and nature of adverse events, with severity determined according to National Cancer Institute (NCI) Common Terminology Criteria for Adverse Events, Version 5.0 (CTCAE v5.0) • Safety laboratory values • Vital signs • ECG

 • Evaluate the safety of switching from atezolizumab SC to atezolizumab IV and from atezolizumab IV to atezolizumab SC 	
 • Incidence, severity, and nature of adverse events, with severity determined according to NCI CTCAE v5.0 during the study Treatment Cross-over Period by treatment arm • Safety laboratory values during the study Treatment Cross-over Period by treatment arm • Vital signs during the study Treatment Cross-over Period by treatment arm • ECG during the study Treatment Cross-over Period by treatment arm
Exploratory Pharmacokinetic Objective	Corresponding Endpoint

 • Characterize the exposure of atezolizumab when given intravenously or subcutaneously 	
 • Serum atezolizumab concentration at specified timepoints during SC and IV administration
Exploratory Immunogenicity Objective	Corresponding Endpoints

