1.2.1 Treatment Assignment

This is a randomized, open-label study. After written informed consent has been obtained, all screening procedures and assessments have been completed, and eligibility has been established for a participant, the study site will obtain the participant's identification number and treatment assignment from the interactive voice or web-based response system (IxRS).

Participants will be randomly assigned to one of two treatment arms: Arm A (atezolizumab SC followed by atezolizumab IV) or Arm B (atezolizumab IV followed by atezolizumab SC). Randomization will occur in a 1:1 ratio through use of a permuted-block randomization method to ensure a balanced assignment to each treatment arm. Randomization will be stratified by disease stage (II, III, IV) and type of surgery (no surgery, pneumonectomy, any other lung surgery).

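### The planned PK summaries by randomised arm and cycle mix SC and IV exposure at Cycles 8 and 16 and at later discontinuation visits, so they cannot describe exposure by route after Cycle 6 (minor)

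*SAP*

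**What the plan says.** The exploratory PK objective in SAP 1.1, Table 2 is framed by route: "Characterize the exposure of atezolizumab when given intravenously or subcutaneously". Its endpoint is "Serum atezolizumab concentration at specified timepoints during SC and IV administration".

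The analysis in SAP 4.4.3 is framed by sequence. Concentrations are tabulated "by treatment arm and cycle, when appropriate and as data allow", and "Individual and median serum atezolizumab concentrations will be plotted by treatment arm and day". Protocol 6.6 says the same. SAP 1.2.1 defines Arm A as SC then IV, and Arm B as IV then SC.

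Protocol 3.1.1 fixes the switch: "At Cycle 4, participants will cross-over and receive atezolizumab administered according to the alternative route of administration". It then hands the choice to the participant: "After Cycle 6, participants will select how they would like atezolizumab to be administered (SC or IV) for the Treatment Continuation Period".

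Protocol Appendix 2 schedules PK samples at Cycle 1 (pre-dose and Day 4), pre-dose on Day 1 of Cycles 2 to 6, 8 and 16, and at the treatment discontinuation visit. There is no Cycle 7 sample.

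**The concern.** The objective asks about exposure under each route, while the display groups by sequence. During the crossover period sequence and cycle together determine route, so the two agree. Once participants choose for themselves, the arm label says nothing about how the last dose was given. A by-arm mean or median at Cycle 8 or 16 then averages troughs after SC 1875 mg and after IV 1200 mg in unstated proportions.

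At stake is whether the only scheduled long-term troughs can be read by route. The matter is not confined to the final report: SAP 4.1 bases the primary analysis, PK included, on all data up to the clinical cut-off, so some samples from Cycle 8 onwards can appear there too.

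**Working it through.** The plan states no figure for this point, so there is none to reproduce. The check maps each scheduled pre-dose sample to the dose it reflects, then sizes the mixing.

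**Step 1: route of the preceding dose** (Protocol 3.1.1 and Appendix 2)

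| Pre-dose sample | Reflects dose of | Arm A | Arm B |
|---|---|---|---|
| Cycle 2 | Cycle 1 | SC | IV |
| Cycle 3 | Cycle 2 | SC | IV |
| Cycle 4 | Cycle 3 | SC | IV |
| Cycle 5 | Cycle 4 | IV | SC |
| Cycle 6 | Cycle 5 | IV | SC |
| Cycle 8 | Cycle 7 | own choice | own choice |
| Cycle 16 | Cycle 15 | own choice | own choice |

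Every cell through Cycle 6 holds one route, barring deviations or the move to IV that Protocol 4.3.2.1 allows after SC toxicity. Cycle 4 is also a pure cell. Its only oddity is that a first-route trough sits under the first second-route cycle. The Cycle 8 and 16 cells are mixed in both arms, as are discontinuation samples from participants who stop in the continuation period.

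**Step 2: size of the mixing**

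Inputs:
- r, the SC:IV trough ratio: 1.05, 90% CI 0.88 to 1.24 (Protocol 1.4.4, Phase III part of IMscin001, Cycle 1 trough at 1875 mg SC and 1200 mg IV). Carrying it to later cycles is an assumption.
- p, the share choosing SC: 70%, borrowed from the assumed preference rate in SAP 2.2. The documents give no rate for the route chosen, so 50% to 90% is also shown.

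The geometric mean of a mixed cell relative to IV is r^p:

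| r | p = 50% | p = 70% | p = 90% |
|---|---|---|---|
| 0.88 | 0.938 | 0.914 | 0.891 |
| 1.05 | 1.025 | 1.035 | 1.045 |
| 1.24 | 1.114 | 1.163 | 1.214 |

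At p = 70% and r = 1.05 the cell is 1.05^0.7 = 1.035, which is 3.5% above IV. Relative to SC it is 1.05^(0.7 − 1) = 0.985, or 1.5% below. Across the interval at p = 70% the cell runs from 8.6% below to 16.3% above IV.

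**Step 3: what the arm contrast shows**

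The expected Arm A to Arm B ratio is r^(pA − pB). If the same share chooses SC in both arms, the exponent is 0 and the ratio is 1.0 whatever r is. The by-arm display at Cycles 8 and 16 then carries no information on route.

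**Step 4: group sizes after a split by route**

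Taking the 126 evaluable participants of SAP 2.2 as an illustration gives 63 per arm. At p = 70%, 63 × 0.7 is about 44 SC and 19 IV. The range is 32 and 31 at 50%, and 57 and 6 at 90%, all before attrition.

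**The case against.** The best defence is that SAP 4.4.3 is a qualified sentence for an exploratory analysis. It allows judgement on when a summary is appropriate, reports individual concentrations and foresees possible population PK modelling. All of that is true, but none of it commits to a split by route. The as-received rule in SAP 4.1 belongs to the safety analyses. SAP 4.3.1 does split dosing exposure by route in the continuation period, but that is not carried over to PK.

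A second objection is that grouping by last route does not give clean long-term data either. This stands in part. The Cycle 8 sample follows a single self-chosen dose after three doses by the Cycle 4 to 6 route, so for participants who changed route at Cycle 7 it is not a settled trough. The groups are also self-selected, and the IV group may be small. These are reasons to label the display carefully. They do not favour pooling.

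Three stronger readings are tempting, and the documents support none of them.
- A reader might infer that the Cycle 4 sample is charged to the wrong route. The plan tabulates by arm and cycle, the sample is scheduled as pre-dose, and the cell is homogeneous. The risk is one of labelling only.
- A reader might infer that comparison with earlier studies is lost. The trough comparisons in Protocol 1.4.4 and 3.3.1 concern Cycle 1. Here that is the Cycle 2 pre-dose sample, where Arm A is all SC and Arm B all IV.
- A reader might take the troughs in Protocol 3.3.1 and compute 0.7 × 121.1 + 0.3 × 76.0 = 107.6 µg/mL, which is 42% above IV. Those are Cycle 1 values from two different studies, and the SC value is for 1800 mg of a pharmacy-mixed product. The randomised ratio of 1.05 at this trial's doses is the relevant input.

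**Conclusion.** The point holds for Cycles 8 and 16 and for treatment discontinuation samples taken after Cycle 6. If the stated grouping is followed, those summaries pool the two routes and cannot answer an objective defined by route. Through the Cycle 6 pre-dose sample the by-arm display is sound.

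The likely numerical distortion is small: about 3.5% above IV, with a range of about −9% to +16%. This rests on the borrowed 70% choice rate, on a Cycle 1 ratio applied to later cycles, and on treating the trough as set by the last route alone, which is least secure at Cycle 8. The grouping problem itself rests on none of these assumptions.

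Severity is minor. The objective is exploratory and descriptive, and no primary or safety conclusion depends on it.

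**What to change.** In SAP 4.4.3:
- Keep the tables and plots by arm and cycle for Cycles 1 to 6. Add a footnote that each pre-dose sample reflects the preceding dose, so that Cycle 4 pre-dose is the trough of the Cycle 3 route.
- Summarise and plot Cycles 8, 16 and treatment discontinuation by the route of the last dose before the sample.
- Label those groups descriptive and self-selected.
- At Cycle 8, show whether the participant changed route at Cycle 7.

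The cost is a wording change and one derived variable from dosing records already collected. No new samples, visits or participants are needed. The price is that the IV group may be small after Cycle 6.

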4.4.4 Exploratory Immunogenicity Analyses

The immunogenicity analyses will be based on the ADA-evaluable population.

Participants will be grouped according to treatment received or, if no treatment is received prior to study discontinuation, according to treatment assigned.

The numbers and proportions of ADA-positive participants and ADA-negative participants at baseline (baseline prevalence) and after drug administration (post-baseline incidence) will be summarized by treatment group. When determining post-baseline incidence, participants are considered to be ADA positive if they are ADA negative or have missing data at baseline but develop an ADA response following study drug exposure (treatment-induced ADA response), or if they are ADA positive at baseline and the titer of one or more post-baseline samples is at least 0.60 titer unit greater than the titer of the baseline sample (treatment-enhanced ADA response).

Participants are considered to be ADA negative if they are ADA negative or have missing data at baseline and all post-baseline samples are negative, or if they are ADA positive at baseline but do not have any post-baseline samples with a titer that is at least 0.60 titer unit greater than the titer of the baseline sample (treatment unaffected).

Descriptive analysis of safety and PK may be analyzed by ADA status.

4.4.5 Health Status Utility

Health economic data will be assessed by the EQ-5D-5L. The results from the health economic data analysis will be reported separately from the CSR.

4.5 INTERIM ANALYSES

No interim analyses will be planned.

5. SUPPORTING DOCUMENTATION

This section is not applicable since there is no additional supporting document.

